If the Sponsor decides to terminate the study early, the Sponsor will inform the Investigators of the reason for early study termination. It is the responsibility of the Investigators to inform their IRB as applicable according to local and national laws/regulations.

9. **Modification of the Protocol**

All amendments to this clinical protocol shall be agreed to by the Sponsor and be recorded with a justification for the amendment prior to implementation. Approval of

the applicable IRB must be obtained prior to implementation, if required according to the local and/or national laws/regulations.

E. Medical Events/Adverse Events Definitions and Classifications

An adverse event is any unfavorable or unintended sign, symptom, or disease associated with the use of the study device, whether or not related to the device. Adverse event is synonymous with complication or medical event. All medical events, regardless of classification, are required to be reported on the Adverse Event Report case report form. The completed **Adverse Event Report** must be submitted to the Sponsor in a timely manner. The Investigator or Designee will also promptly provide the Sponsor with any additional requested information required for Sponsor to comply with regulatory requirements. If applicable per their reporting requirements, the Investigator or Designee will also report applicable adverse event(s) to their IRB.

1. Classification of the Event

Adverse Event (AE) [1]:

An Adverse Event is defined as any untoward medical occurrence, unintended disease or injury, or untoward clinical signs (including abnormal laboratory findings) in subjects, users or other persons, whether or not related to the investigational medical device.

Note 1: This definition includes events related to the investigational medical device or the comparator.

Note 2: This definition includes events related to the procedures involved.

Note 3: For users or other persons, this definition is restricted to events related to investigational medical devices.

Serious Adverse Event (SAE) [1]:

A Serious Adverse Event is any adverse event that

- a. led to death
- b. led to serious deterioration in the health of the subject, that either resulted in:
 1. a life-threatening illness or injury, or
 2. a permanent impairment of a body structure or a body function, or
 3. in-patient or prolonged hospitalization, or
 4. medical or surgical intervention to prevent life-threatening illness or injury or permanent impairment to a body structure or a body function
- c. led to fetal distress, fetal death or a congenital abnormality or birth defect.

Note: Planned hospitalization for a pre-existing condition, or a procedure required by the protocol, without serious deterioration in health, is not considered a serious adverse event.

Adverse Device Effect (ADE) [1]:

An Adverse Device Effect is an adverse event related to the use of a medical device.

Note 1: This definition includes adverse events resulting from insufficient or inadequate instructions for use, deployment, implantation, installation, or operation, or any malfunction of the medical device.

Note 2: This definition includes any event resulting from use error or from intentional misuse of the medical device.

Serious Adverse Device Effect (SADE) [1]:

A Serious Adverse Device Effect is an adverse device effect that has resulted in any of the consequences characteristic of a serious adverse event.

The Sponsor is responsible for determining the final classification of adverse events.

If an Unanticipated Serious Adverse Device Effect (USADE) is identified it will be promptly reported to concerned Investigators and regulatory authorities as required by applicable regulatory requirements. If applicable per their reporting requirements, the Investigator or Designee will report the USADE to their IRB.

2. Intensity of Symptoms

Mild:

The subject is aware of the sign or symptom, but finds it easily tolerated. The event is of little concern to the subject and/or little clinical significance. The event is not expected to have any effect on the subject's overall health or well-being.

Moderate:

The subject has discomfort enough to cause interference with or change in usual activities. The event is of some concern to the subject's health or well-being and may require medical intervention and/or close follow-up.

Severe:

The event interferes considerable with the subject's usual activities. The event is of definite concern to the subject and/or poses substantial risk to the subject's health or well-being. The event is likely to require medical intervention and/or close follow-up and may be incapacitating or life threatening. Hospitalization and treatment may be required.

NOTE: The term “severe” refers to the intensity of the event and can be used with any event, without regard to whether or not it meets the criteria for being classified as “serious” or “unanticipated”. For example, a subject can have a severe headache, but it is not a serious event.

3. Relation to Device

Not Related:

There is no possible relationship between the adverse event and the implanted device.

Uncertain:

It is not known if there is a possible relationship between the adverse event and the device.

Probably:

There is a reasonable possibility that the adverse event was caused by the device.

Definitely:

There is no doubt the adverse event is directly related to the device.

Medical Device Information Reporting

For any adverse event with a relation to device of “Uncertain”, “Probably” or “Definitely”, a **Medical Device Reporting Information Form** (MDRIF, Appendix E) must be completed and submitted to the Study Manager within 7 days. Other required supporting documentation that should be sent with the MDRIF:

- All subject x-rays
- Operative notes
- A summary detailing the subjects postoperative physical therapy regimen
- Subject activity level at the time the event occurred.

4. Outcome Definitions

The outcome is in relationship to the Adverse Event, not the treatment rendered for the event (if any).

Resolved:

The adverse event has been resolved and/or no further treatment is required to treat the reported condition or illness.

Tolerated:

The adverse event will most likely never be resolved. The subject “tolerates” the illness or condition as a matter of life.

Pending:

Treatment or diagnostic studies were prescribed for the adverse event and the outcome of the adverse event is not yet known.

Study Withdrawal:

Due to the adverse event, the subject was withdrawn from the study.

Device Revision/Removal:

The adverse event resulted in the removal of a study device.

Death:

The outcome indicates the subject died as a direct result of the reported adverse event.

Reoperation of Affected Joint:

The adverse event resulted in reoperation of the study joint, but the reoperation did not include removal of a study device.

5. Collection Approach

The type of approach taken to collect adverse event information, whether systematic or non-systematic.

Systematic:

Based on checklists, questionnaires, or tests

Non-Systematic:

Based on spontaneous reporting and recording

F. Monitoring of the Study

Prior to initiating the clinical study, the Sponsor will conduct a site initiation visit to ensure the Investigator(s) and study staff understand the study protocol and requirements and have adequate time and resources to implement and conduct the study. Prior to study initiation, the Investigator must have a fully executed CTA and IRB approval of the study protocol and the study Informed Consent.

During the course of the study, the Sponsor will conduct periodic central monitoring and maintain contact with the study staff to monitor compliance and evidence of adverse events, in accordance with the Sponsor's policies and procedures. The Sponsor will address any identified non-compliance with the executed CTA, study protocol, and applicable regulatory requirements.

If onsite monitoring visit(s) are deemed appropriate by the Sponsor, the Investigator will permit representatives of the Sponsor's monitoring team to have direct access to inspect all source data/documents, study documents/binders, corresponding sections of study subject medical/hospital records, and any other documents relevant to the study. All Sponsor visits (including site initiation) will be documented using the **Monitoring Visit Log** (Appendix C).

XI. Risk Analysis

This post-market clinical study is classified as minimal risk [2] and there are no anticipated risks specific to study participation other than the potential loss of confidentiality. There are no experimental procedures in this study, and participation in this study is not anticipated to affect the medical treatment of enrolled subjects.

The *NexGen* knee components being studied are post-market, non-investigational devices cleared by the FDA via 510(k). The subjects included in this study could receive the devices without participating in the study.

- *NexGen* TM Monoblock Tibia (K012866, K020295, and K031462)
- *NexGen* TM Modular Tibia (K072160)

When used in accordance with product labeling, the risks associated with the use of *NexGen* cementless knee components are similar to those of standard, metal-on-polyethylene cementless knee systems used for the same clinical indication or purpose. These risks are categorized below as either general surgical risks or risks associated with a cementless total knee arthroplasty procedure/study device. Unanticipated adverse events can also occur.

A. General Surgical Risks

General surgical risks and post-operative adverse events can occur with any surgery and include, but are not limited to:

- Anesthetic complications/reactions
- Bleeding and/or excessive blood-loss
- Transfusion reaction
- Chronic Pain
- Post-operative infection
- Vascular injury
- Delayed wound healing
- Deep vein thrombosis (DVT)
- Nerve injury
- Death

B. Risks Associated with Cementless Total Knee Arthroplasty/Study Device

Potential adverse events associated with cementless total knee arthroplasty include, but are not limited to:

- Loosening or fracture/damage of the prosthetic knee components or surrounding tissues.
- Dislocation and/or joint instability.
- Malalignment of the prosthetic knee components.
- Bone fracture or nerve damage.
- Swelling or infection.
- Leg length discrepancies.
- Poor range of motion.
- Pain.
- Venous thromboembolic disease.
- Inflammation.
- Metal sensitivity.
- Corrosion of metal components (the significance and long-term implications are uncertain and await further clinical evidence and evaluation).
- Wear debris can initiate osteolysis which may result in loosening of the implant.

Minimization of Risk

Complications and/or failure of prosthetic implants are more likely to occur in patients with unrealistic functional expectations, heavy patients, physically active patients, and/or with patients who fail to follow through with the required rehabilitation program. Physical activity or trauma can result in loosening, wear, and/or fracture of the implant. The patient must be counseled about the capabilities of the implant and the impact it will have on his or her lifestyle. The patient must be instructed about all postoperative restrictions, particularly those related to occupational and sports activities and about the possibility that the implant or its components may wear out, fail or need to be replaced. The implant may not last the rest of the patient's life, or any particular length of time. Because prosthetic implants are not as strong, reliable, or durable as natural, healthy tissues/bones, all such devices may need to be replaced at some point.

XII. Statistical Considerations

Performance of the commercially available *NexGen TM Monoblock Tibia* and *NexGen TM Modular Tibia* used in primary cementless tibia total knee arthroplasty will be evaluated for radiographic parameters, pain and function, and survival of the device. Data collected in this study will be summarized descriptively and descriptive summaries will be the basis of any study reports issued. These summaries may be used for interim study reports and may also be used to support regulatory submissions, presentations, and/or publications. Additional surgical technique and instrumentation data may be collected and evaluated.

A. General Statistical Methods

Statistical methodology will consist of summarizing collected data descriptively. Categorical data (e.g., gender or race) will be summarized using counts and percentages, and 95% Confidence Interval (CI), over the time periods of interest. Continuous data, such as age, will be summarized by using means, medians, standard deviation, minimum, maximum, and 95% CI over the time periods of interest. Implant survival and return to function will be summarized using a Kaplan-Meier method and presented with rates (as percentages) and confidence intervals.

B. Sample Size

A minimum of 132 subjects are to be enrolled in this study, with approximate equal distribution of at least 66 *NexGen TM Monoblock* and 66 *NexGen TM Modular* subjects. The *NexGen TM Monoblock Tibia* and *NexGen TM Modular Tibia* are considered 2 single-arms being analyzed separately. Sample size is based upon 6 to 10 sites enrolling between 22 to 30 subjects per site.

Based on *NexGen*'s expected success rate of 98% at two years on the primary endpoint and using a 10% non-inferiority margin against a 98% performance goal, 57 subjects are required to achieve 80% power to test non-inferiority. 57 subjects also allow the Sponsor to control the Type-1 alpha error at 0.05. Assuming a 12% loss to follow-up over 2 years, approximately 66 subjects need to be enrolled for each single arm.

XIII. References

- [1] ISO 14155:2011(E). Clinical investigation of medical devices for human subjects – Good clinical practice.
- [2] US Food and Drug Administration. eCFR – Electronic Code of Federal Regulations Title 21. Retrieved April 25, 2017, from https://www.ecfr.gov/cgi-bin/text-idx?SID=e0cb187b56d9cb0279bb080f88b8121d&mc=true&tpl=/ecfrbrowse/Title21/21tab_02.pl.

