Demographic Evaluation	X					
Surgical & Discharge Information		X				
Physical Exam	X		X	X	X	X
Physician Assessment of Postop Radiographs		X	X	X	X	X
Subject completed:						
Forgotten Joint Score (FJS-12)	●		●	●	●	●
Oxford Knee Score (OKS)	●		●	●	●	●
UCLA Activity & Satisfaction Survey	●		●	●	●	●
Site completed as applicable:						
Adverse Event Report		★	★	★	★	★
Protocol Deviation	★	★	★	★	★	★
Study Completion	★	★	★	★	★	★
Explanted Device Form			★	★	★	★

Activity	Preop	Immediate Postop	6 Weeks Postop	6 Months Postop	1 Year Postop	2 Years Postop
Radiograph Submission		X	X	X	X	X

- X Site completed (Investigator or designee)
- Subject completed
- ★ Site completed as applicable (Investigator or designee)

The following table indicates required forms to be completed by the site for revision patients:

Form Name	Comments
Physician Assessment of Postop Radiographs	Mark the “Pre-Revision” exam period.
Adverse Event Report	Document adverse event resulting in the revision.
Study Completion	Complete indicating “Study Prosthesis Removed” under Study Completion Status.
Explanted Device Form	Document explanted device information. Send explanted device to Zimmer Biomet per Appendix F.
Medical Device Reporting Information Form (MDRIF):	If device-related, complete MDRIF form (Appendix E) and forward the form and all applicable supporting documents to Zimmer Biomet within 7 days. The supporting documents include: 
 ▪ Operative reports (index and revision surgery) ▪ Radiographs (immediate postop, intermediate, and pre-revision)

IV. Introduction and Purpose

In recent years the advent of highly porous trabecular metal implants in cementless fixation has brought the cemented vs. cementless debate back to the forefront among surgeons when determining best practices and benefits to patients. Fricka, et al [3], describe the potential benefits of cementless fixation as preservation of bone stock, shorter operating room time (and thus a cost savings), ease of revision if necessary, and elimination of any complications associated with cemented fixation such as third body wear and retained loose fragments. Potential disadvantages are the lack of surgeon experience implanting the modular tibial tray, cost of such implants, and determining if there is an ideal patient population for implantation of such devices.

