Each Principal Investigator will be responsible for obtaining Institutional Review Board (IRB) approval as required prior to conducting the study. In order to avoid potential selection bias, each Investigator will offer study participation to each consecutive eligible patient presenting as a candidate for primary cementless tibia total knee arthroplasty using the *NexGen* TM Monoblock or *NexGen* TM Modular Tibia. Eligible candidates who express interest in study participation will be offered Informed Consent. All potential study subjects will be required to participate in the Informed Consent process and will not be considered enrolled in the study until the candidate has signed and dated the IRB approved Informed Consent Form. Study data cannot be collected until the candidate has completed the Informed Consent process and signed and dated the IRB approved Informed Consent Form.

All study subjects will undergo preoperative clinical evaluations prior to their cementless tibia total knee arthroplasty. An immediate postoperative radiograph will be required. Postoperative clinical follow-up and radiographic evaluations will be conducted at 6 weeks, 6 months, 1 year, and 2 years.

The Investigator will review radiographs immediately postop and at each clinical evaluation to ensure the radiographs meet the protocol requirements. The Sponsor will provide a radiographic protocol (Appendix D) to assist sites in proper x-ray technique in order to assure adequate images are captured for study analysis.

The Sponsor will request copies of these radiographs for independent radiologic review. The Sponsor will request one central reviewer for all radiographs independent of the surgeon and institution.

VII. Study Population

The study population for primary statistical analysis will be comprised of subjects who require primary cementless tibia total knee arthroplasty and satisfy the inclusion/exclusion criteria outlined in this section of the protocol. In order to avoid potential selection bias, Investigators will offer study participation to each consecutive eligible patient presenting as a candidate for primary cementless tibia total knee arthroplasty using the commercially available *NexGen* TM Monoblock or *NexGen* TM Modular Tibia implants. Eligible candidates who express interest in study participation will be offered Informed Consent. The **Inclusion/Exclusion Criteria** should not be completed until the study-specific Informed Consent Form has been completed.

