NexGen knee components included in this study are the *NexGen* TM Monoblock Tibia or *NexGen* TM Modular Tibia. Both the *NexGen* TM Tibias are designed specifically to adhere to bone through the use of trabecular metal technology. These devices are intended for long-term implantation in accordance with product labeling. Please refer to the package insert for additional information and instructions.

IX. Study Procedures

A. Offer Study Participation

Study participation will be offered to each consecutive eligible patient presenting as a potential candidate for primary cementless tibia total knee arthroplasty using the commercially available *NexGen* TM Monoblock or *NexGen* TM Modular Tibia implants, depending on the clinical site's

device designation. A **Subject Enrollment Log** (Appendix C) will be completed to document all individuals screened as potential candidates for the study. Eligible candidates who express interest in study participation will be offered Informed Consent. Prior to patient involvement in the study, the patient must participate in the Informed Consent process and sign and date the IRB approved Informed Consent Form.

B. Informed Consent Process

For candidates that express interest, the Investigator or Designee will describe relevant study information, including the purpose, procedures, possible risks, and potential benefits associated with study participation. The Investigator or Designee will also review, along with the candidates, the Informed Consent Form approved by both the governing IRB and the study Sponsor.

Candidates shall have sufficient time to read and understand the IRB approved Informed Consent Form and discuss whether they wish to participate in the study. Candidates will be asked to acknowledge whether all of their questions and concerns have been addressed to their satisfaction. Any questions that candidates may have will be addressed appropriately by the Investigator or Designee. Candidates will be further instructed that they are free to obtain additional information from the Investigator or Designee at any time, that they are free to decline participation, and that they are free to withdraw their consent and discontinue their participation at any time without prejudice.

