Clinical Interval	Interval Window in Days Postop*	Approximate Window in Weeks or Months Postop
6 weeks	28 to 56 days	± 2 weeks
6 months	151 to 214 days	± 1 month
1 year	333 to 396 days	± 1 month
2 years	669 to 791 days	± 2 months

*Visit(s) outside of window will be determined based on Days Postop

Postoperative follow-up clinical data will be collected on the following source document forms:

1. Physical Exam
2. Physician Assessment of Postop Radiographs
3. Forgotten Joint Score
4. Oxford Knee Score
5. UCLA Activity & Satisfaction Survey
6. Adverse Event Report (as applicable)
7. Protocol Deviation (as applicable)
8. Study Completion (as applicable)
9. Implanted Device Form (as applicable)

Subjects will be followed postoperatively for 2 years. Unless the study is otherwise closed, data will continue to be collected until the subject completes the study per the protocol, voluntarily withdraws from the study, is withdrawn from the study by the investigator, is lost to follow-up, undergoes revision to remove a study device, or expires. See Management of Incurrent Events (Section X, Subsection D of this protocol) for additional details. Reason(s) for study completion must be documented on the **Study Completion** form.

K. Minimization of Subjects Lost to Follow-up

Subject follow-up is extremely important for the conduct of a clinical study, and the expectation is to maintain the highest possible rate of follow-up compliance throughout this study. During the informed consent process and at each follow-up interval, subjects should be counseled on the importance of completing future study follow-up intervals.

L. Radiographic Definitions and Methods

All postoperative radiographs will be evaluated by the Investigator and documented using the **Physician Assessment of Postop Radiographs**. An **Adverse Event Report** must be completed for findings identified as an adverse event.

It is the Investigator's responsibility to review radiographs for image quality during the subject's clinical visit and prior to uploading into the image collection service. Radiographic images must show an orthogonal view of the tibial implant interface. If the Sponsor determines a radiograph is of poor quality, then the site must reschedule the subject for additional radiographs.

1. Required radiographic views

Radiographic Interval	Interval Window	Required Radiograph
Immediate Postop	Pre weight-bearing	AP and Lateral
6 weeks	± 2 weeks	AP and Lateral

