Adverse Events, Serious Adverse Events, Adverse Device Effects, and Serious Adverse Device Effects will be documented on the **Adverse Event Report** throughout this study, including information on the date of onset, treatment and resolution, as well as assessment of both the seriousness and the relationship to the study device. The outcome of complications will be documented and changes in outcome are to be updated during the course of the study. In case of early termination of this study, further follow-up of the subject shall proceed according to the hospital's standard procedure.

Device Deficiencies that did not lead to an adverse event but could have led to a medical occurrence if suitable actions had not been taken, if intervention had not been made, or if circumstances had been less fortunate, shall be reported to the Sponsor as soon as possible, as well.

See Section X, Subsection E of this protocol for additional information regarding adverse event classifications. All medical events, regardless of classification, are required to be reported on the **Adverse Event Report**. The completed **Adverse Event Report** must be submitted to the Sponsor in a timely manner. The Investigator or Designee will also promptly provide the Sponsor with any additional requested information required for the Sponsor to comply with regulatory requirements. If applicable per their reporting requirements, the Investigator or Designee will also report applicable adverse event(s) to their IRB.

3. Revision

Study subjects will be study completed for any revision, regardless of the component being revised. In the event that removal of one or more of the implanted knee components is necessary, the Investigator will determine the best treatment and/or revision method for the subject.

Prior to revision surgery, the Investigator or qualified Designee must document radiographic findings on the **Physician Assessment of Postop Radiographs**.

Once the revision surgery has been completed, the Investigator or qualified Designee must complete an **Adverse Event Report** as well as a **Study Completion** form terminating the subject from the study. For the study completion status, select "Study Prosthesis Removed".

All explanted device information must be documented on an **Explanted Device Form**. In addition, all explanted devices must be returned to Zimmer Biomet using the **Explant Procedure** (Appendix F).

4. Investigator Withdrawal

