The Investigator can choose to withdraw a subject from the study if the subject no longer meets study inclusion/exclusion criteria. The reason for the Investigator's withdrawal of the subject must be documented on the **Study Completion** form.

5. **Subject Withdrawal**

Study subjects may choose to withdraw from the study at any time, for any reason. If possible, a final evaluation will be completed for any subject who no longer wishes to participate in the study. The reason for the subject withdrawal must be documented on the **Study Completion** form.

6. **Lost to Follow-up**

A study subject will be considered lost to follow-up after they have missed a visit and attempts to locate and evaluate the subject using the procedure outlined below have failed. All attempts to contact the subject are to be documented in the subject's medical record and on the **Study Completion** form. Missed visit(s) also must be documented using the **Protocol Deviation** form, unless the visit is retrospective. The first three contact attempts should be made by telephone, with additional attempts as outlined in the following table:

If	Then
a response is not received after three (3) phone calls	the Investigator or Designee should send a letter to the subject explaining the follow-up agreement per the Informed Consent, and requesting a response from the subject.
all attempts to contact the subject are unsuccessful or the subject is contacted and chooses to withdraw from the study	a Study Completion form will be completed and will specify the reason the subject is no longer participating in this study.

7. **Protocol Deviations**

Investigators should not deviate from the study protocol. If a protocol deviation does occur, the deviation must be documented on the **Protocol Deviation** form and submitted to the Sponsor. If applicable per their reporting requirements, the Investigator or Designee will also report applicable protocol deviations to their IRB.

8. **Study Termination**

Study subject participation is expected to end upon completion of the subject's 2 year follow-up visit unless the subject voluntarily withdraws from the study, is withdrawn from the study by the Investigator, is lost to follow-up, undergoes revision to remove a study device, or expires. Reason(s) for study completion must be documented on the **Study Completion** form.

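### The protocol gives two rules for which revisions end follow-up, and the supplied text does not say how a knee revised before 2 years counts in the primary endpoint

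*Combined protocol and SAP*

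**What the plan says.** **Which revisions end participation.** Section X.D.3 (Revision) is broad: "Study subjects will be study completed for any revision, regardless of the component being revised". It tells sites to select the completion status Study Prosthesis Removed, and the table of forms for revision patients in Section III uses the same status. Section IX.J (Postoperative Follow-up Data Collection) is narrower. Its list of reasons for ending data collection closes with a subject who "undergoes revision to remove a study device, or expires". Section X.D.8 (Study Termination) repeats this: "is withdrawn from the study by the Investigator, is lost to follow-up, undergoes revision to remove a study device, or expires".

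**What the study device is.** The synopsis lists only the Monoblock and Modular tibias as study devices. Section VIII agrees: "NexGen knee components included in this study are the" two tibial designs. Section X.E.4 has a separate adverse-event outcome for the case where "The adverse event resulted in reoperation of the study joint, but the reoperation did not include removal of a study device".

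**What is analysed.** The primary endpoint is absence of progressive tibial radiolucencies at 2 years, with the definition left to the radiographic protocol (Appendix D, not among the supplied text). Freedom from revision for any reason and OKS above 38 are separate secondary endpoints. Section VII defines the analysis population by eligibility: "The study population for primary statistical analysis will be comprised of subjects who require primary cementless tibia total knee arthroplasty". Section XII makes descriptive summaries the basis of reports and plans a Kaplan-Meier summary of implant survival. Non-inferiority appears only in Section XII.B.

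**The concern.** There are two separate problems.

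First, a site that revises a femoral or other non-tibial component and leaves the study tibia in place cannot follow both rules. X.D.3 ends participation, while IX.J and X.D.8 do not list the event as a reason to end. Under X.D.3 the knee loses its 2-year film although the tibia under study is still implanted. If Study Prosthesis means the tibia, the completion code is also inaccurate.

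Second, a knee whose participation ends at a revision before 2 years cannot supply the film that the primary endpoint needs. The reason it is missing may be the failure that the endpoint is meant to detect: a tibia revised for loosening is the clearest case. Such a knee could be counted as a failure, classified from an earlier film, or left out, and these choices can give opposite answers. The supplied text does not choose among them. The eligibility-based population in Section VII favours keeping the knee in the denominator but assigns it no outcome. OKS above 38 at 2 years has the same gap.

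**Working it through.** **Inputs, all from Section XII.B.** Expected success 98%; performance goal 98% with a 10-point margin, so the bound is 98 − 10 = 88%; power 80%; alpha 0.05, sidedness not stated; 57 required per arm; 12% loss to follow-up; 66 enrolled per arm. The documents give no revision rate, so every revision count below is an assumption.

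**Reproducing the plan's figure.** One-sample normal approximation:

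n = [z(1−α)·√(p0(1−p0)) + z(0.80)·√(p1(1−p1))]² / (p1−p0)²

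With p0 = 0.88, p1 = 0.98 and one-sided α = 0.025, n = 56.96, rounded up to 57. One-sided α = 0.05 gives 42.6. The stated 57 therefore corresponds to one-sided 0.025. For enrolment, 57/0.88 = 64.8, so 65 would suffice and 66 is consistent with the plan's approximate figure.

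**Size of the first problem (revision with the tibia retained).** Expected evaluable knees are 66 × 0.88 = 58.08, about one above 57. Assume such terminations come on top of the 12% allowance. Normal-approximation power at 98% true success is:

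| Evaluable knees | Power |
|---|---|
| 57 | 80.0% |
| 56 | 78.7% |
| 55 | 77.3% |

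Two terminations in an arm leave about 56 knees and three leave about 55. The loss is small.

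**Size of the second problem: one arm, three ways of counting.** Take 57 knees, two of them tibias revised before 2 years, and one radiographic failure among the other 55. P is the exact one-sided binomial probability of at least that many successes at 88%; z = (p̂ − 0.88)/√(0.88 × 0.12/n).

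| Revised knees are | Result | Rate | Exact P | z |
|---|---|---|---|---|
| counted as failures | 54/57 | 94.7% | 0.077 | 1.57 |
| left out | 54/55 | 98.2% | 0.0075 | 2.32 |
| counted as successes on an earlier film | 56/57 | 98.2% | 0.006 | 2.38 |

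The first row misses the bound and the other two meet it, whether the test is exact at one-sided 0.025, exact at one-sided 0.05, or the normal approximation with z ≥ 1.96. Leaving out a single revised failure is a borderline case: 54/56 gives exact P = 0.029 and z = 1.94, which passes only at one-sided 0.05.

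**How far the reported rate moves.** If a share q of failures is revised and left out, the expected observed success is p/(1 − (1−p)q), and 57(1−p)q knees are lost.

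| q | True 98%: observed (knees lost) | True 88%: observed (knees lost) |
|---|---|---|
| 0 | 98.0% (0) | 88.0% (0) |
| 10% | 98.2% (0.1) | 89.1% (0.7) |
| 25% | 98.5% (0.3) | 90.7% (1.7) |
| 50% | 99.0% (0.6) | 93.6% (3.4) |

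**Chance of wrongly meeting the bound when true success is 88%.** Failures F ~ Bin(57, 0.12), revised failures R ~ Bin(F, q), and the test is applied to 57 − R knees. With the normal approximation at one-sided 0.025, the rule that reproduces 57, the probability is 2.6, 2.8, 4.2 and 14.1% for q = 0, 10, 25 and 50%. The exact test at one-sided 0.025 gives 0.6, 1.2, 3.1 and 13.6%. These are stress cases, ten points below the expected rate.

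**The case against.** **X.D.3 is the dedicated revision clause and should govern.** It is explicit, the Section III table agrees with it, and IX.J and IX.M both refer readers to Section X.D. A site would probably follow it. But X.D.8 is itself inside X.D and carries the narrower wording, so the cross-reference does not settle the matter. What stands is that this part is mostly a wording repair with little effect on power.

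**The completion code need not be wrong.** Study Prosthesis is undefined and could mean the whole knee, and the Explanted Device Form records what was removed. This stands: tibial and other revisions can still be told apart. The reoperation category in X.E.4 is an adverse-event outcome code. It shows that the protocol recognises surgery without removal of a study device, but it does not itself contradict X.D.3.

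**The films exist.** X.D.3 requires a pre-revision assessment, the Section III table requires immediate postoperative, intermediate and pre-revision films in device-related cases, and Section VI says: "The Sponsor will request one central reviewer for all radiographs independent of the surgeon and institution". This stands. What is missing is a classification rule for these knees.

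**Revision is already a separate endpoint.** Revisions would still show there and in the Kaplan-Meier summary. That limits what a reader of the full report could miss, but it does not correct the primary rate.

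**Stronger readings that a reader might infer.** One is that the plan has no rule at all. The documents do not support that, because Appendix D was not supplied. Section VI describes it as guidance on x-ray technique but also defers the radiolucency definition to it. Another is that the plan excludes revised knees and so inflates success. Nothing supplied says they are excluded, and the Section VII population points the other way. A third is that error rates of 14% or so are to be expected. Those need 88% true success and half of all failures revised within 2 years, and no revision rate is documented.

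**Conclusion.** The concern holds in two limited parts. The text conflict is real, is confined to revisions that leave the study tibia in place, and costs one to three points of power if two or three such knees per arm fall outside the 12% allowance. The missing counting rule matters more, because following X.D.3 as written makes outcome data missing for a reason tied to the outcome. If revised knees drop out, the primary rate is overstated, and in an arm of 57 the handling of two knees can decide whether the 88% bound is met.

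The size is conditional. Near 98% true success, or with few failures revised, the reported rate moves by one percentage point or less. The verdict rests on the supplied text alone, on assumed revision counts, and on the non-inferiority comparison in XII.B being used. Because Section XII bases reports on descriptive summaries, the first effect would be on the reported rate and its confidence interval. The point should be fixed before data are reviewed; confidence is medium because Appendix D is unseen.

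**What to change.** 1. Reconcile X.D.3, IX.J, X.D.8 and the completion status in X.D.3 and Section III, so that one rule says which revisions end data collection and the code matches what was removed. Which rule to adopt is for the sponsor to decide.
2. State in Section XII, or cite Appendix D if it already has the rule, that knees revised before 2 years stay in the primary denominator and that a study tibia revised before 2 years counts as not achieving the primary endpoint.
3. Add a sensitivity analysis in which only revisions for fixation failure or loosening count as failures.
4. Do not count a knee without a 2-year film as a 2-year success on an earlier clean film alone. Report it as missing and show both extremes, all such knees as failures and all as successes.
5. State the matching rule for OKS above 38.

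**Cost.** The change is to wording and tabulation, and N is unchanged. The reported success rate may fall slightly. Power falls only if counted revisions take true success below the assumed 98%, but it is sensitive there: at n = 57 the normal approximation (one-sided 0.025) gives 80.0% at 98% and 59.9% at 97%. The sponsor should therefore confirm that the 98% assumption already allows for revised tibias.
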